1. BACKGROUND

The MEB, as the Reference Member State (RMS) for SEROQUEL and SEROQUEL XR, requested AstraZeneca to update the education materials in scope of the EU Risk Management Plan (RMP) and Summary of Product Characteristics (SmPC) changes with respect to hyperglycaemia and metabolic monitoring. The content and the messages for these educational materials have been agreed and distribution in the individual member states is ongoing.

AstraZeneca was also requested to provide a plan for assessing the effectiveness of these educational materials. During discussion with the MEB, it was communicated that there are 2 components to the assessment of effectiveness: process indicators (receipt and understanding of materials) and outcome indicators (changes in behaviour and effect on patients). To realize these 2 indicators, AstraZeneca is proposing 2 components for the evaluation of the effectiveness of the metabolic education: an objective, easy to understand and complete healthcare provider survey and the use of an Electronic Medical Records approach, as a potential means to assess the monitoring of patients.

This protocol describes the evaluation of the effectiveness of the distribution of metabolic educational materials sent to healthcare providers in the EU. It will be conducted via an evaluation survey that uses a questionnaire to assess the receipt of the educational material, whether the material was read, and to assess healthcare provider behaviour regarding the conduct of monitoring of metabolic parameters for patients treated with SEROQUEL and SEROQUEL XR. The survey will be conducted among healthcare providers who were targeted to receive the educational materials following local guidance and directives.

A companion proposal describes the evaluation of electronic medical record (EMR) data including details on objectives, the source of data, and the target healthcare provider-base for the database assessment.

2. OBJECTIVES OF THE EVALUATION SURVEY

The healthcare provider survey is a questionnaire that will document the receipt of educational materials and assess the behaviour of healthcare providers around the following key metabolic monitoring messages communicated through the educational materials.

The key messages communicated in the educational materials are presented below.

Information on weight and hyperglycaemia has been updated in the "Special Warnings and Precautions" section of the label:

Weight:

Weight gain has been reported in patients who have been treated with Seroquel® or Seroquel® XR, and should be monitored and managed as clinically appropriate as in accordance with utilised antipsychotic guidelines*.

Hyperglycaemia:

Hyperglycaemia and/or development or exacerbation of diabetes mellitus occasionally associated with ketoacidosis or coma has been reported rarely, including some fatal cases (see section 4.8). In some cases, a prior increase in body weight has been reported which may be a predisposing factor. Appropriate clinical monitoring is advisable in accordance with utilised antipsychotic guidelines. Patients treated with any antipsychotic agent including Seroquel® or Seroquel® XR, should be observed for signs and symptoms of hyperglycaemia, (such as polydipsia, polyuria, polyphagia and weakness) and patients with diabetes mellitus or with risk factors for diabetes mellitus should be monitored regularly for worsening of glucose control. Weight should be monitored regularly.

Existing information on other metabolic parameters include the following:

Lipids:

Increases in triglycerides, LDL and total cholesterol, and decreases in HDL cholesterol have been observed in clinical trials with Seroquel® or Seroquel® XR. Lipid changes should be managed as clinically appropriate.

Metabolic Risk

Given the observed changes in weight, blood glucose (see hyperglycaemia) and lipids seen in clinical studies, there may be possible worsening of the metabolic risk profile in individual patients, which should be managed as clinically appropriate.

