3.1.1 Questions Regarding Key Monitoring Behavior

Question 1:

What is your medical specialty*? Please select one from the drop-down list below.

- O General Medicine/General Practice
- O Neurology
- O Psychiatry
- O Other SPECIFY:

* NOTE – OTHER SPECIALTIES TO BE INCLUDED BASED ON AUDIENCES TO WHOM MATERIAL WAS SENT

Question 2

Please think about your patients with schizophrenia, bipolar disorder, and/or major depressive disorder who are treated with Seroquel® or Seroquel® XR. Describe the "monitoring" of metabolic factors^{*} potentially related to treatment with Seroquel® or Seroquel® XR.

A. What proportions of your patients are being monitored by you, someone else in your practice or are referred to other healthcare providers? _____%

B. What proportion of your patients is referred to other healthcare providers for monitoring?

*Monitoring of metabolic factors includes: weight at initiation and during continuing treatment, ordering or reviewing lipid panel tests, observing patients for signs or symptoms associated with hyperglycaemia, ordering or reviewing tests for blood glucose measurement for patients with diabetes mellitus or in patients with risk factors for diabetes mellitus for worsening of glycaemic control, and counseling on nutrition, exercise and maintaining a healthy lifestyle

Question 3

Thinking now of the patients that you (or someone in your practice) monitor for metabolic issues potentially related to treatment with Seroquel® or Seroquel® XR, which of the following activities do you do? Please check all that apply.

- [□] I counsel patients taking Seroquel® or Seroquel® XR on healthy eating, exercise, and healthy lifestyle improvements
- ^D I monitor patients' weight at the initiation of treatment with Seroquel® or Seroquel® XR
- ^a I monitor patients' weight on a regular basis after initiating treatment with Seroquel® or Seroquel® XR
- I monitor tests for hyperlipidemia in patients who are taking Seroquel or Seroquel® XR
- [□] I observe for signs and symptoms of hyperglycaemia in patients who are taking Seroquel® or Seroquel® XR
- I monitor patients with diabetes mellitus or with risk factors for diabetes mellitus for worsening of glucose control if they are taking Seroquel® or Seroquel® XR

Question 4

The following question has two parts; please respond to both parts of the question.

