3.3 Sample Size

A sample size of 100 completed questionnaires from healthcare providers in each of eight selected countries representing the geographic diversity of the EU is proposed. The size of the sample was determined based on both practical and statistical considerations. There is no presumed target rate for success in risk minimization measures based upon either a process measure (e.g., receiving educational materials) nor is there a rate specified *a priori* for success in outcome measures (e.g., metabolic monitoring). A sample of 100 completed questionnaires will allow estimation of the rate for process and outcome measures with a moderate degree of precision (within 6-10 percentage points regardless of the actual level of the process or outcome measure). The table below shows the precision of the estimates for level process and outcome measure using two-sided 95% confidence intervals (CIs) obtained with the sample size of 100 completed surveys. The noted CIs are used to indicate that for any survey-estimated level of effectiveness of risk minimization, the true population level of effectiveness is at least as high as the lower limit of the 95% CI and may be as high as the upper limit of the 95% CI.

Table 1:Precision of estimated Rates of effectiveness of risk minimization
including: 1) Receiving information (as Process measure) or 2)
performance of metabolic monitoring (as Outcome measure) with a
Sample Size of 100 (Two-sided 95% Confidence Interval)

Estimated Rate	95% Confidence Interval Lower Limit	95% Confidence Interval Upper Limit
1%	0.0%	3%
6%	1.3%	10.7%
11%	4.9%	17.1%
16%	8.8%	23.2%
21%	13%	29%
26%	17.4%	34.6%

Estimated Rate	95% Confidence Interval Lower Limit	95% Confidence Interval Upper Limit
31%	21.9%	40.1%
36%	26.6%	45.4%
41%	31.4%	50.6%
46%	36.2%	55.8%
51%	41.2%	60.8%
56%	46.3%	65.7%
61%	51.4%	70.6%
66%	56.7%	75.3%
71%	62.1%	79.9%
76%	67.6%	84.4%
81%	73.3 %	88.7%

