6. ANALYSIS

The survey questionnaire contains questions about the specialty of the physician sample completing the survey, questions specific to whether referrals are made to other healthcare providers for metabolic monitoring, whether the healthcare provider conducts monitoring of patients, general questions regarding receipt of the educational materials, and behavior about reading the materials. Information obtained from responses to each question of the survey will be reported as descriptive statistics. A frequency distribution of responses to each question (the number of respondents who give answers to each response option) will be presented.

Each risk minimization behavior will be evaluated individually.

Related behaviors, such as:

- Monitoring for weight
- Monitoring for signs and symptoms of hyperglycaemia and monitoring blood glucose changes in patients with diabetes mellitus will be combined to report the number of survey respondents who answered each risk minimization activity individually, any one activity and both activities. This will be expressed as a percent of the total number of respondents who answered the questions on these risk minimization activities.

Frequency distributions of the responses to having received SEROQUEL[®] / SEROQUEL[®] XR educational materials and behaviors about reading the educational materials, will also be calculated and displayed. The analysis of frequencies will include exact binomial 95% confidence intervals.

The following will be reported, as appropriate, as part of this analysis:

- The number of invitations issued to healthcare providers
- The number of healthcare providers screened for participation
- The number of healthcare providers eligible for participation
- The number of healthcare providers who completed the survey

- Description of healthcare provider survey participants, including:
 - Specialty of respondent
 - Country of practice
- Frequency distribution of responses to each survey question (the number of respondents who give each answer to each question)
- Percent of respondents selecting desired response to each question relating to each risk minimization activity and 95% confidence interval
- Percent of respondents demonstrating success of composite risk minimization activities and 95% confidence interval

Additional analyses may be performed as needed.

Risk Minimization Physician Survey Protocol

Drug Substance	Quetiapine fumarate
Study Code	D1443C000127
Edition Number	1

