Appendix B Questionnaire

QUESTIONNAIRE

The questionnaire is designed to be administered as an on-line survey via Internet. The following are mock-up version of what the successive screens that would be displayed

Screen 3 Question 1:

What is your medical specialty*? Please select one from the drop-down list below.

- O General Medicine/General Practice
- O Neurology
- O Psychiatry
- O Other SPECIFY:

* NOTE – OTHER SPECIALTIES TO BE INCLUDED BASED ON AUDIENCES TO WHOM MATERIAL WAS SENT

Screen 4 Question 2:

Instructions: Please think about your patients with schizophrenia, bipolar disorder, and/or major depressive disorder who are treated with Seroquel® or Seroquel® XR. Describe the "monitoring" of metabolic factors^{*} potentially related to treatment with Seroquel® or Seroquel® XR.

- What proportions of your patients are being monitored by you, someone else in A. your practice or are referred to other healthcare providers? %
- What proportion of your patients is referred to other healthcare providers for B. monitoring? %

*Monitoring of metabolic factors includes: weight at initiation and during continuing treatment, ordering or reviewing lipid panel tests, observing patients for signs or symptoms associated with hyperglycaemia, ordering or reviewing tests for blood glucose measurement for patients with diabetes mellitus or in patients with risk factors for diabetes mellitus for worsening of glycaemic control, and counseling on nutrition, exercise and maintaining a healthy lifestyle

Screen 5 Question 3:

Instructions: Thinking now of the patients that you yourself monitor for metabolic issues potentially related to treatment with Seroquel® or Seroquel® XR, which of the following activities do you perform? Please check all that apply.

GEL Version ID: CNS.000-362-594.2.0 Approved Date Printed: 04-Jan-2013 Approved by [name] 21 Dec 2012 15:02:47

- ^a I counsel patients taking Seroquel® or Seroquel® XR on healthy eating, exercise, and healthy lifestyle improvements
- I monitor patients' weight at the initiation of treatment with Seroquel® or Seroquel® XR
 I monitor patients' weight on a regular basis after initiating treatment with Seroquel® or
- Seroquel® XR
- [□] I monitor tests for hyperlipidemia in patients who are taking Seroquel or Seroquel® XR
- I observe for signs and symptoms of hyperglycaemia in patients who are taking Seroquel® or Seroquel® XR

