I monitor patients with diabetes mellitus or with risk factors for diabetes mellitus for worsening of glucose control if they are taking Seroquel® or Seroquel® XR

Screen 6 Question 4:

Instructions: The following question has two parts; please respond to both parts of the question

- A. Did you receive educational information relevant to the issues in this survey from AstraZeneca, either as a mailing or from a company representative, in (INSERT LOCAL MARKET REFERENCE MONTH) 2012 regarding the Product Label for Seroquel® or Seroquel® XR?
 - O Yes
 - O No
 - O Do not know/not sure

B. Did you read the educational information?

- O Yes
- O No
- O Do not know/not sure

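### The Question 3 glucose item leaves out the word 'regularly' that the hyperglycaemia message contains, so a tick does not show that the message is followed and the reported percentage can be too high

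*Protocol*

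**What the plan says.** Protocol Section 2 says the survey will assess provider behaviour around the key messages of the educational materials. On glucose the message is that "patients with diabetes mellitus or with risk factors for diabetes mellitus should be monitored regularly for worsening of glucose control". It has two elements: who is monitored (patients who have diabetes or risk factors for it) and how (regularly).

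The matching check box in Question 3 reads "I monitor patients with diabetes mellitus or with risk factors for diabetes mellitus for worsening of glucose control" for those taking the product. The wording is the same in Section 3.1.1 and in Appendix B. Question 3 treats weight differently. One box covers weight at the start of treatment, and a second covers "weight on a regular basis after initiating treatment".

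The footnote to Question 2 describes glucose monitoring as "ordering or reviewing tests for blood glucose measurement for patients with diabetes mellitus or in patients with risk factors for diabetes mellitus", with both groups and no frequency.

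Section 6 will report the "Percent of respondents selecting desired response to each question relating to each risk minimization activity and 95% confidence interval". It gives as an example of behaviours to be combined "Monitoring for signs and symptoms of hyperglycaemia and monitoring blood glucose changes in patients with diabetes mellitus".

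**The concern.** Hyperglycaemia is one of the two label topics, with weight, that Section 2 lists as updated. The percentage ticking the glucose box is therefore one of the main behavioural results of the survey.

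The item follows the message almost word for word but leaves out the adverb that says how the monitoring is to be done. A respondent who looks at glucose now and then, or only when something prompts it, is not doing what the message asks and can still tick honestly. The same percentage then covers followers and irregular monitors, and nothing else in the questionnaire tells them apart. An analysis plan cannot repair this, because the frequency was never asked.

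The Section 6 label adds a smaller mismatch. A result titled as monitoring in patients with diabetes would not describe an item that also asks about patients at risk.

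**Working it through.** **Step 1. Compare the wording.**

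| Place | Patients named | Frequency term |
|---|---|---|
| Section 2, message | diabetes or risk factors | *regularly* |
| Question 2 footnote | diabetes or risk factors | none |
| Question 3 glucose item (Section 3.1.1 and Appendix B) | diabetes or risk factors | none |
| Question 3 follow-up weight item | all treated patients | present |
| Section 6 composite | diabetes only | none |

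The message and the item agree on the patients and differ on frequency. The footnote does not restore the frequency, and neither does Section 6. The composite differs from both the message and the item on the patients.

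**Step 2. Reproduce the plan's precision.** Section 3.3 plans "A sample size of 100 completed questionnaires from healthcare providers in each of eight selected countries". Table 1 follows from p ± 1.96 × √(p(1 − p)/100), with the lower limit cut at zero:

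- p = 51%: 1.96 × √(0.51 × 0.49/100) = 9.8 points, giving 41.2% to 60.8%, as printed.
- p = 81%: 1.96 × √(0.81 × 0.19/100) = 7.7 points, giving 73.3% to 88.7%, as printed.

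All 17 rows reproduce. The exact intervals planned in Section 6 are similar (51%: 40.8% to 61.1%; 81%: 71.9% to 88.2%). At n = 100 the sampling half-width is about 10 points at most. These figures do not depend on item wording, so they neither support nor contradict the concern.

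**Step 3. How the omission would act (illustration only).** Let t be the true share of providers who follow the message and f the share of the others who still tick. Neither is given in the documents. Assume that every follower ticks. Then

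observed rate = t + f(1 − t), and excess = f(1 − t).

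| t | f = 10% | f = 25% | f = 50% |
|---|---|---|---|
| 40% | 46% | 55% | 70% |
| 60% | 64% | 70% | 80% |
| 80% | 82% | 85% | 90% |

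The excess runs from 0.10 × 0.20 = 2 points to 0.50 × 0.60 = 30 points. The formula does not contain n, so more questionnaires would narrow the interval without moving its centre towards t. The range only shows how sensitive the result is to assumed inputs. It is not an estimate for this survey.

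**The case against.** Several points on the other side are sound.

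- **The *or* is not a fault of the item.** A reader might infer that joining the two groups in one box lets providers off half the message. The *or* is taken unchanged from the message, where it naturally covers both groups. A provider who follows only patients with known diabetes might tick, but nothing shows that such a tick is meant to count as adherent.
- **One test is a strained example.** The item asks about monitoring for worsening, which implies comparison over time. This weakens the idea that a single test justifies a tick. Occasional or prompted monitoring remains, and the item does not exclude it.
- **The contrast with weight has a structural reason.** The second weight box needs a time phrase to differ from the first. This explains why the phrase is there, but does not supply the one missing for glucose.
- **Scoring is open.** A reader might infer that non-followers are counted as giving the desired response. Section 6 does not define that response for this item, so the text supports only that they *can* be counted.
- **The net direction is not proven.** The missing word can only push the rate up. However, Appendix B limits Question 3 to patients whom the respondent personally monitors, while Section 3.1.1 includes others in the practice. Respondents whose colleagues do the monitoring may leave the box blank, which pushes the rate down.
- ***Regularly* is itself undefined.** Respondents would still interpret it. That is equally true of the message and of the weight item, and using the same word at least makes the item ask what the message says.
- **The survey is not the only evidence.** Section 1 mentions a companion assessment of electronic records as a potential means of assessing monitoring. That does not make this item's percentage valid.

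The Section 6 phrase is best read as a short label for two Question 3 boxes. It removes nobody from the data, so the mismatch there is one of wording.

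**Conclusion.** The concern holds in a limited form. The glucose item omits the frequency element of the message it is meant to measure, nothing elsewhere in the protocol restores it, and no later analysis can recover it. A tick therefore does not establish adherence to the hyperglycaemia message, and through this omission the reported percentage can overstate adherence. The Section 6 composite should also name the same patients as the item.

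The documents give no basis for the size. The 2 to 30 points above rest entirely on assumed values of t and f and on every follower ticking. A reader might infer that the error must exceed the sampling uncertainty of about 10 points. That is possible under some of these assumptions and false under others, and the documents do not decide it. The point does not affect the sample size or Table 1.

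**What to change.** In Section 3.1.1 and Appendix B, insert *regularly* between *I* and *monitor* in the item that begins "I monitor patients with diabetes mellitus or with risk factors for diabetes mellitus for worsening of glucose control". In Section 6, change the composite so that its glucose part names both patient groups, as the item does.

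Splitting the item into one box per group is optional. If it is split, adherence should not require both ticks unless a no-such-patients option is added. Section 3.2.1 admits providers who only might prescribe the product, and a provider with no patients in one group would otherwise be scored as non-adherent.

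The cost is one word in the item, in two places, and a small edit to Section 6. Section 4.1.2 puts translation after validation of the questionnaire, so the change is cheapest before that work starts. The reported rate may come out lower.

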3. METHODOLOGY

This protocol and the accompanying physician survey were designed by AstraZeneca.

3.1 Study Design

This survey will be completed by a sample of healthcare providers who were targeted to receive the metabolic educational materials and either currently prescribe or have the potential to prescribe SEROQUEL or SEROQUEL XR. A sample of healthcare providers who were targeted for the educational materials will be approached to participate in the survey.

The survey will be administered using the following modality:

• Self-administered and Internet-based questionnaire accessed through a secure website instructing the participant to enter a unique code provided in the invitation.

The survey will begin with screening questions to confirm respondent eligibility to participate in the survey. Completion of the entire survey is expected to take less than 10 minutes.

The survey included in Appendix B is written to reflect the wording and screen-by-screen presentation of questions for an Internet-based survey administration.

All respondents who complete the survey and who provide their contact information will be mailed a fee consistent with approved market value for the physician's time for completing the survey.

The questions related to having received the educational materials and having read the information (measures of process) are closed-ended questions (answered affirmatively as yes/no/unsure response options). Questions related to physician behavior regarding monitoring of patients (measures of outcome) are percentage estimates provided by the physician.

